2.1 Objectives & Hypotheses	<h3>2.1 Objectives and Aims</h3> 
Aims
 
1. To evaluate the determinants of Sustained Virologic Response (SVR) in patients treated with grazoprevir and elbasvir in the presence of immunosuppression (post-renal transplant). 
Primary Objective
 
1. To determine the difference in the host immune response as measured by interferon stimulated gene (ISG) expression (IP-10 in particular), and HCV specific T-cell response in post-renal transplant patients compared to historical, non-transplant patients and its association with SVR.2. To examine the efficacy of grazoprevir and elbasvir in patients post- renal transplantation compared to historical, non-transplant patients. 
Secondary Objectives
 
1. To evaluate the safety and adverse events of grazoprevir and elbasvir post-renal transplant patients compared to historical, non-transplant patients.2. To describe the effects of chronic HCV treatment on two-year renal allograft outcomes in patients treated after renal transplantation. <h4>2.1.1 Clinical hypotheses</h4> 
Primary Hypotheses
 
1. Patients treated for chronic HCV with grazoprevir and elbasvir after renal transplantation will maintain a robust host immune response as measured by ISG expression (IP-10 in particular) and HCV specific T cell responses in the presence of immunosuppression.2. The proportion of patients who achieve SVR12 will be greater than 90% in post-renal transplant patients. 
Secondary Hypotheses
 
1. The safety, tolerability, and adverse events of treatment with grazoprevir and elbasvir in patients with chronic kidney disease will not be significantly different in post-transplant patients compared to non-transplant patients.2. The treatment of chronic HCV using grazoprevir and elbasvir will improve the renal allograft outcomes in terms of rejection or graft survival. <h4>2.1.2 Clinical Impact</h4> 
Chronic HCV in patients with CKD is associated with an increased risk of death as well as renal transplant graft failures (1). With the FDA approval of grazoprevir and elbasvir, we now have a regimen that can be used in these patients with severe CKD. However, it remains unknown if there is an immunologic advantage for both achievement of SVR 12 and renal allograft outcomes in treating these patients prior to their transplant compared to waiting until after transplantation when they will be immunosuppressed. And while we predict that transplant recipients will maintain high rates of SVR, it is uncertain whether these immunosuppressed transplant recipients will maintain robust host immune responses to HCV treatment.

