Additionally, the effect of immunosuppression on the host response to HCV therapy is unknown. On the one hand, these patients could be treated for hepatitis C infection prior to renal transplantation to avoid the impact of immunosuppression as well as the impact of HCV-related liver and kidney disease on allograft function post transplantation. On the other hand, this approach will eliminate access to HCV positive kidneys (making the wait list time longer) and potentially reduce the efficacy of DAA therapy (due to drug-drug interaction between calcineurin inhibitors and HCV drugs). Recent studies have shown that grazoprevir is a weak inhibitor of CYP3A4 and may increase tacrolimus levels (approx. 40% above expected), though change has not been seen in elbasvir or grazoprevir levels (19) (8).

There are real benefits in waiting to treat HCV in patients until after transplantation in that it could decrease the wait time for transplantation by not necessitating a delay in transplant while completing HCV therapy and by permitting the use of HCV-positive kidney donors. Showing the impact that immunosuppression has on the host immune response to HCV during therapy would enable clinicians to decide whether patients should be treated before or after transplant, especially in cases where the wait for a transplant may be quite long.

2.3 Study Design	Experimental design The study will be a pilot, prospective, single-center, open-label, non-randomized, non-controlled clinical trial. 25 HCV genotype 1 infected post-renal transplant patients will be enrolled in the study. Recruitment will be conducted through the renal transplant and nephrology outpatient clinics at the University of Maryland.
-------------------------	--

Study population

The study will involve a single cohort of post-renal transplant patients.

All patients will have HCV genotype 1 chronic infections with active viremia and have no cirrhosis at the time of enrollment. All patients will additionally have stable renal function.

[figure not shown]
The post-transplant patients will include renal transplant recipients of both living donor and deceased donor organs infected with HCV prior to their transplantation with stable GFRs and active HCV viremia. These patients will also be recruited from the University of Maryland's multidisciplinary transplant nephrology clinic.

Inclusion criteria

- At least 18 years of age at the time of screening

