
form of a completed CIOMS I/MedWatch within two (2) business days of learning of the information. SAE reports and any other relevant safety information are to be forwarded to Merck's Global Safety group [contact]. SAE and Reportable New Information will be reported to the IRB as per University policy.

All reports of Study Drug exposure during pregnancy or lactation, whether associated with an AE or not, must be reported to Merck's Global Safety group in accordance with the timelines and contact information for an SAE. Principal Investigator shall follow pregnancies to term to obtain the outcome of the pregnancy. The outcome of the pregnancy shall be forwarded to Merck's Global Safety group.

Clinical labs will also be drawn at these visits. There is a known, defined drug interaction between grazoprevir and tacrolimus causing an increase in tacrolimus levels of approximately 40%, as documented in the package insert (22). Levels of immunosuppressive agents will also be determined at these visits as clinically indicated. The need for dose modification of the patient's immunosuppression in the time between visits will be recorded.

End of treatment visit

Patients will be seen 12 weeks after starting study drugs (and 16 weeks in the case of genotype 1a patients with baseline NS5A RAVs) for an end of study visit. Patients will also be counseled about study adherence and we will inquire about adverse events. A complete panel of tests that will be performed during this visit is detailed in Appendix 1.

Post treatment follow up visits

Patients will be followed 12 weeks after they complete treatment. A complete panel of tests that will be performed during this visit is detailed in Appendix 1.

Additionally, patients may be enrolled in an ongoing study titled "A prospective cohort study to assess treatment efficacy in chronic hepatitis C mono-infection and co-infection with HIV" (HP – 00063362), to monitor longer-term outcomes. Outcomes including graft survival and episodes of rejection will be monitored by periodic medical record abstraction.

Early termination or treatment discontinuation

Patients who discontinue HCV therapy prior to 12 weeks will be followed at post-treatment week 4 and post-treatment week 12. HCV VL, safety labs and hepatic panel will be performed at these visits. A complete panel of tests that will be performed during this visit is detailed in Appendix 1.

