In brief, peripheral T-cells will be isolated from PBMCs by Ficollhypaque density gradient separation and be stimulated with pooled HCV genotype specific peptides. For this experiment, we will use HCV 15-18-mer peptides with 11 or 12 amino acid overlaps spanning the entire HCV polyprotein and reconstituted in 5% sterile dimethylsulphoxide (DMSO), pooled consecutively into twenty-one groups and aliquoted until use. The number of HCV-responsive IFN- γ -producing PBMCs will be quantified by a standard ELISPOT assay (BD Biosciences), in which 96 well ELISPOT plates are coated with anti-IFN- γ biotinylated capture antibody and incubated overnight at 4°C. Plates will be blocked using a lymphocyte medium, and PBMCs will be allowed to rest for 6 hours at 37°C. PBMCs will then be plated between 250,000- 400,000 cells per well with either phytohaemagglutinin (PHA) as a positive control (5 mg/ml), DMSO as a negative control (0.05%), or pooled HBV peptides (3 mg/ml/peptide). All cultures will be performed in duplicate. After incubating for 12 hours at 37°C, cells will be removed, and plated with streptavidin detection antibody, enzyme conjugate, and substrate. The plates will then be air dried in the dark overnight, and developed spots will be enumerated using an ELISPOT plate reader.

2.6 Study Duration	We anticipate the entire study duration to be 24 months. The duration per study subject enrolled will be 30 to 34 weeks depending on their treatment duration. This will include 6 weeks of screening, 12 to 16 weeks of therapy, and 12 weeks of follow up to determine SVR 12 (Figure 1).
---------------------------	---

	
After the initial 30-34 weeks, patients will be enrolled in our ongoing HCV treatment cohort study (HP – 00063362). Using this long term prospective cohort study, we will be able to follow our patients' longer-term outcomes through medical record abstraction.

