
2.7 Statistical Analysis and Sample Size Justification
	
Data analysis will be completed by the study biostatistician.
 
Primary Endpoints
 
Primary Objective 1. The primary endpoint for this objective will be the measurement of host immune responses using ISG expression including IP-10 levels, and HCV specific T-cell responses. ISG expression and IP-10 levels will be measured before and 4 weeks after completion of therapy. HCV specific T-cell responses will be measured before and during SVR 12 (12 weeks after completion of the study medications).
 
Primary Objective 2. The primary endpoint for this objective will be the measurement of SVR 12. This will be measured at study week 24/28, or 12 weeks after completion of the study medications.
 
Secondary Endpoints
 
Secondary Objective 1. We will assess the safety of the medications using adverse event monitoring. The primary endpoint for this objective will be the presence of any severe adverse event. A secondary endpoint will be the early discontinuation of the study medications. This will be assessed at the study visits weeks 0, 4, 8, and 12. Based upon prior trials with these investigational drugs, we estimate rate of serious adverse events of about 15% (17).
 
Secondary Objective 2. The primary endpoint for this objective will be episodes of rejection and graft survival for post-transplant patients after treatment and will be recorded via medical record abstraction as part of their enrollment in the ongoing prospective cohort study to assess treatment efficacy in chronic hepatitis C (HP – 00063362).
 
Research data will be collected and managed using REDCap (Research Electronic Data Capture) hosted at the University of Maryland, which is a secure, web-based application to support data capture for research studies. All of these variables will be entered into REDCap by study staff at the end of each study visit based upon the labs obtained, patient questionnaires, and interim records reviews, and after the initial 30 to 34 weeks of the study based upon medical records reviews.
 
Statistical Methods
 
Clinical treatment arm
 
All statistical analyses will be based on an intention-to-treat model, including all enrolled patients who received at least one dose of study medication. Both the primary efficacy and safety endpoints will be based on the proportion of patients with SVR 12 and severe adverse events, respectively, with point estimates and 95% confidence interval. Both primary efficacy and safety endpoints will be compared to a non-transplant, HCV-infected historical control group by using two-sided, exact one-sample binomial test at a significance level of 0.05. Demographic and baseline characteristics will be summarized using standard descriptive statistics overall and by patient cohort. Univariate logistic regression will be performed to identify baseline factors associated with SVR 12 at a significance level of 0.05.
 
Measurement of host immune response

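### Secondary Hypothesis 2 claims improved graft outcomes that a single uncontrolled cohort cannot show, and the plan does not say that graft records will cover every dosed patient

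*Combined protocol and SAP*

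**What the plan says.** Secondary Hypothesis 2 in 2.1.1 is directional: "The treatment of chronic HCV using grazoprevir and elbasvir will improve the renal allograft outcomes in terms of rejection or graft survival". The objective it belongs to, Secondary Objective 2 in 2.1, is "To describe the effects of chronic HCV treatment on two-year renal allograft outcomes in patients treated after renal transplantation".

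On design, 2.3 says "The study will be a pilot, prospective, single-center, open-label, non-randomized, non-controlled clinical trial" and "The study will involve a single cohort of post-renal transplant patients". The comparison group in 2.7 is historical and non-transplant: 25 patients with stored blood samples. It is used for SVR12, severe adverse events and the immune markers.

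On data capture, 2.7 defines the graft endpoint as "episodes of rejection and graft survival for post-transplant patients after treatment and will be recorded via medical record abstraction as part of their enrollment"; what is meant is joining a separate cohort study (HP-00063362). On joining that study, 2.5.1 says "patients may be enrolled in an ongoing study titled" and 2.6 says "patients will be enrolled in our ongoing HCV treatment cohort study". On the analysis set, 2.7 says "All statistical analyses will be based on an intention-to-treat model, including all enrolled patients who received at least one dose of study medication".

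Two other statements bear on capture. Section 2.5.1 adds that graft survival and rejection will be followed by abstracting medical records at intervals. Section 2.7 says that study variables will go into REDCap, including from record reviews after the first 30 to 34 weeks.

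**The concern.** There are two linked problems.

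The first is the claim. Improvement needs a reference, and the plan supplies none for grafts. If the hypothesis stays as worded, a low rejection or graft-loss rate in 25 treated patients can be presented as support for a treatment benefit that the trial never measured.

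The second is who contributes to the rate. If graft events are known only for patients who join the other study, the denominator is not the dosed population that 2.7 requires. If joining is related to how the graft is doing, the rate is biased, and the plan asks for no count of complete records that would reveal it.

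The two-year period also has no stated starting point. The endpoint in 2.7 is placed after treatment, but the text does not say whether the two years run from first dose, last dose or the SVR12 visit.

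**Working it through.** The plan gives no figure for the graft endpoint, so there is none to reproduce. Its one precision statement (±0.18 at 25 per arm) concerns the difference in SVR12. The check is mainly a comparison of passages.

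**Is there a reference for improvement?**
- Concurrent control: none; 2.3 describes one treated, non-controlled cohort.
- Historical group: non-transplant (2.7), so rejection and graft survival do not exist in it.
- Patients' own past: no before-after analysis is planned. Entry also requires stable renal function (2.3), so the period before treatment is selected to be free of graft loss.
- External rate: 2.1.2 says HCV is associated with graft failure but gives no rate, and 2.7 sets no benchmark.
- Analysis: 2.7 names no estimate, comparison or time point for the graft endpoint.

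No route to an improvement claim remains.

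**Does capture match the analysis set?**
- Set required by 2.7: all dosed patients.
- Set with the endpoint recorded, under the definition in 2.7: patients enrolled in the other study.
- The two agree only if everyone joins, which 2.6 says and 2.5.1 does not.
- Adverse event collection is no substitute: under 2.9.4.1 it stops when participation ends, or 30 days after withdrawal.

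**How much of the two years depends on chart abstraction?** SVR12 is measured at study week 24 or 28 (2.7). With two years taken as 104 weeks from first dose:
- 104 − 24 = 80 weeks, and 80/104 = 77%
- 104 − 28 = 76 weeks, and 76/104 = 73%

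About three quarters of the period lies beyond the last study visit.

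**What could partial capture do?** Assume j non-joiners and 2 patients with an event among the joiners. Neither number is in the documents. The reported rate is 2/(25 − j). The rate in all 25 lies between 2/25 (no non-joiner has an event) and (2 + j)/25 (every non-joiner has one).

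| Non-joiners (assumed) | Reported rate | Possible rate in all 25 |
|---|---|---|
| 3 | 2/22 = 9.1% | 2/25 to 5/25 = 8–20% |
| 5 | 2/20 = 10.0% | 2/25 to 7/25 = 8–28% |
| 8 | 2/17 = 11.8% | 2/25 to 10/25 = 8–40% |

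The upper ends are extremes, not predictions.

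**Precision with full capture.** The Clopper-Pearson 95% limits for x events in 25 are the 2.5% point of Beta(x, 26 − x) and the 97.5% point of Beta(x + 1, 25 − x). For x = 0 the lower limit is 0 and the upper limit is 1 − 0.025^(1/25) = 13.7%.

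| Events | 95% interval |
|---|---|
| 0/25 | 0–13.7% |
| 2/25 | 1.0–26.0% |
| 5/25 | 6.8–40.7% |

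Even complete data give a wide interval, which is acceptable for description.

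**The case against.** The best defence is that the plan already does the sensible thing. The objective is descriptive and 2.7 plans no graft comparison, so no planned analysis would produce an improvement claim. On capture, neither the abstraction sentence in 2.5.1 nor the REDCap sentence in 2.7 carries a joining condition. Patients must also be followed in the university's own clinics (2.3), so their records should generally be at hand.

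Much of this stands. A reader might infer that graft data will be missing for non-joiners. The documents do not show that, and abstraction for everyone is a plausible intention. But the 2.5.1 sentence directly follows the one saying patients may join, 2.6 describes longer-term follow-up as done through the cohort study, and the endpoint definition ties recording to enrolment there. None of these passages says that non-joiners are covered. Nor does the lack of a planned comparison cure a hypothesis that asserts its result.

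Two further readings are tempting and should not be adopted:
- **That two-year outcomes contradict the 24-month study duration in 2.6.** That section gives each subject 30 to 34 weeks and sends later outcomes to the cohort study. The natural reading is that 24 months covers enrolment through SVR12.
- **That the trial fails because 25 patients cannot confirm SVR12 above 90%.** No test against 90% is planned, and 2.7 presents the figure as an anticipation. The answer also depends on the method: at 25/25 the exact 95% lower limit is 0.025^(1/25) = 86.3%, but the Jeffreys lower limit is 90.5%.

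**Conclusion.** The point holds on the text. Secondary Hypothesis 2 asserts an improvement that this design cannot assess and that its own objective does not seek. That conclusion needs no assumption beyond the stated design.

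The capture point is narrower. The passages are inconsistent and leave open a graft rate based on joiners only, against the all-dosed analysis set. Whether this would happen, and how large any bias would be, cannot be known from the documents. The 10% reported against 8–28% possible rests on an assumed 5 non-joiners and 2 events, and shows only that a few non-joiners matter when n is 25. The endpoint is secondary and the repair is cheap, so the change should be made, but the main SVR12 analysis does not depend on it.

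**What to change.** - **2.1.1:** reword Secondary Hypothesis 2 to match its objective, for example: *two-year rejection and graft loss will be described in all dosed patients, with no inference of improvement*.
- **2.5.1, 2.6 and 2.7:** reconcile *may* and *will*. State that record abstraction to two years covers every dosed patient whether or not they join the other cohort, subject to a check of consent and IRB approval.
- **2.7:** count the two years from first dose, and reconcile this with the present placement of the endpoint after treatment. First dose exists for every patient in the analysis set and keeps graft events during treatment in the count. Starting at last dose would leave out graft loss or death on treatment.
- **2.7:** report rejection and graft loss as proportions with exact 95% confidence intervals, and give the number of the 25 with complete two-year records.
- **2.6:** say that abstraction may run beyond the 24 months.
- **Optional, 2.1.1 and 2.7:** present SVR12 above 90% as an expectation, noting that by the exact method even 25/25 leaves a lower limit of 86.3%.

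The cost is a more modest claim, some extra abstraction time, and possibly an amendment if the consent check requires one. No patients or visits are added.

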
2.2 Background & Rationale, Significance of Selected Topic & Preliminary Data

Background

Hepatitis therapy has evolved rapidly from an interferon based, prolonged regimen with moderate efficacy to oral, direct acting antiviral (DAA) based regimens with high efficacy. Recently, sofosbuvir/ledipasvir, as single tablet combination and Viekira pak, a combination pill of multiple DAs, have all been approved for the treatment of hepatitis C in genotype 1 and 4 infected patients. However, limited data exist in the use of either of these regimens in patients with renal disease, particularly those with CKD stages 4 and 5.

Sofosbuvir enters the hepatocyte where it is metabolized to its active form, GS-461203. The downstream inactive nucleoside metabolite GS-331007 is almost exclusively eliminated from the body renally, mediated through a combination of glomerular filtration and active tubular secretion (2). Results of phase II and III clinical trials of sofosbuvir have previously excluded patients with serum creatinine levels greater than 2.5 mg/dL or creatinine clearance (CrCl) level less than 60 mL/min. In subjects with end stage renal disease (ESRD) (relative to subjects with normal renal function), sofosbuvir and GS-331007 AUC (0-inf) were 28% higher and 1280% higher, respectively, when sofosbuvir was dosed 1 hour before hemodialysis compared with 60% higher and 2070% higher, respectively, when sofosbuvir was dosed 1 hour after hemodialysis. No dosage adjustment is required for patients with mild or moderate renal impairment (CrCl 30 mL/min-80 mL/min) (2). Thus, the safety of sofosbuvir has not been established in patients with severe renal impairment (CrCl <30) or ESRD. Unlike with sofosbuvir, no clinically relevant changes in ledipasvir pharmacokinetics were found between volunteers with normal renal function and those with severe renal impairment (eGFR <30 mL/min by Cockcroft-Gault) after a single dose of 90 mg of ledipasvir was administered (3).

HCV-TARGET is an ongoing prospective observational cohort study characterizing the use of DAA agents across clinical practices in North America and Europe. The study reported adverse events and efficacy of sofosbuvir containing HCV treatment regimens in patients with variable degree of renal dysfunction (eGFR <30, 31-45, 46-60 and >60). The patients received different regimens that included sofosbuvir (peg/sof/rbv; sof+ sim ± rbv, sof/rbv). Overall, the regimens were well tolerated with no increased discontinuation among patients with low eGFR. The SVR12 rates were similar across the groups regardless of renal function. Notably, there were progressive deterioration of renal function and renal symptoms in the eGFR <30 ml/min suggesting the need for close monitoring of these patients. In summary, patients with low baseline renal function have a higher frequency of anemia, worsening renal dysfunction and SAEs, while the treatment responses remain high and comparable to those without renal impairment (4).

Viekira Pak consists of paritaprevir/ritonavir, ombitasvir and dasabuvir, all cleared by hepatic metabolism. Single dose pharmacokinetics of paritaprevir/ritonavir, ombitasvir and dasabuvir was evaluated in HCV negative volunteers with mild (eGFR 60-89 ml/min), moderate (eGFR 30-59ml/min) and severe (<30ml/min) renal dysfunction. The results concluded that changes in the pharmacokinetics were not considered to be clinically relevant in HCV infected patients (5). Thus, Viekira Pak remains an option for some patients with CKD. However, there are significant drug-drug interactions between the ritonavir in Viekira Pak, which is a CYP3A inhibitor and tacrolimus, which is a substrate of CYP3A and which a majority of renal transplant patients are on post-transplantation.

Twenty patients with HCV genotype 1 infection and CKD stages 4/5 (eGFR <30 without cirrhosis) were treated with AbbVie 3D ± RBV in a multicenter open-label phase IIb study. Notably, 70% of patients were African Americans and 65% had CKD receiving hemodialysis. Ribavirin (GT1a only) was dosed 4 hours before hemodialysis and monitored with weekly hemoglobin assessments. Though still ongoing, all patients thus far have achieved SVR4 (10/10) and SVR12 (2/2). Interestingly, 8 of 13 patients required

interruption of RBV due to a drop in hemoglobin and 4 of 8 patients also required erythropoietin during the first 7 weeks of therapy. Mean drug concentration (C_{trough}) of all drugs were measured which were within the range that was observed with previous pharmacokinetic studies in healthy volunteers (6). In summary, HCV genotype 1 non-cirrhotic patients treated with AbbVie 3D +/- RBV can result in viral suppression in most patients. However, increased frequency of ribavirin-induced anemia can occur frequently, requiring close monitoring of all patients and judicious dose reductions of RBV. In addition, the use of this ritonavir containing regimen is limited in the renal transplant population due to drug-drug interactions with calcineurin inhibitors.

Recently, the combination of elbasvir/grazoprevir has shown efficacy in both treatment naïve and null responders with chronic HCV genotype 1 infection with or without cirrhosis (7). Both grazoprevir and elbasvir are cleared by hepatic metabolism and hence, could be used in patients with impaired renal function, including renal transplant candidates or recipients. Grazoprevir is a weak inhibitor of CYP3A4 and thus the area under the curve for single-dose tacrolimus increased by approximately 40%, but decreased the C_{max} by approximately 40% (8).

Evaluation of host immune response to treatment

Persistent activation of host inflammation in the liver is partially mediated by endogenous interferons, which contributes to the pathologic development of hepatic fibrosis (9). This activated response is present in both acute and chronic infection; however, it is unable to eradicate HCV (10). Increased mRNA expression of these ISGs in liver biopsy samples is associated with failure of interferon based therapies (11). It has been previously demonstrated that host responses play an important role in achieving SVR in patients with chronic hepatitis C undergoing therapy using DAAs. Clearance of HCV during DAA treatment is associated with a downregulation of type II and III IFNs along with their respective receptors and ISGs and SVR was associated with an increased ISG expression in the liver and IFNA2, which could play a role in eliminating residual HCV (11).

IP-10, an interferon gamma inducible CXC chemokine targeting T lymphocytes and NK cells and monocytes, has been shown to be produced by hepatocytes. Elevated pre-treatment IP-10 levels have been associated with a poorer response to therapy and inability to achieve SVR (12).

In addition to the ISG expression mediated response, T cells also play a role in viral clearance. Enhanced polyclonal CD4+ T cell responses have been found in cleared acute HCV infections and this response persists in those who permanently clear infection (13) (14). In cleared chronic infection, polyclonal and persistent CD4 T-cell responses directed at a variety of different HCV-specific proteins have similarly been detected (13).

Rationale for the study

Host immunity is also likely a major determinant of achieving SVR renal transplant recipients with variable degree of immunosuppression. However, it is unclear what role immunosuppression may play in modulating this host immune response. The modulation of this response by immunosuppression in patients who are post-transplantation could have significant implications for clinical outcomes and achievement of SVR as well as the maintenance of SVR over time. In this regard, we would like to evaluate host response to DAA therapy using grazoprevir and elbasvir in patients with CKD by evaluating three previously well characterized host responses associated with favorable SVR outcomes. These include ISG expression (11), IP-10 levels (15) and HCV specific T-cell responses (16).

A recent study (C-SURFER) evaluated the safety and efficacy of 12 weeks of grazoprevir and elbasvir for HCV genotype 1 patients with CKD stages 4/5. The study was designed to randomize eligible patients to either immediate or deferred treatment with grazoprevir and elbasvir. The delayed treatment arm received placebo and was treated with grazoprevir and elbasvir subsequently. The study participants were HCV genotype 1, CKD stages 4/5 (eGFR <30), and 76% were on hemodialysis, and 46% were African Americans. A small number of patients with compensated cirrhosis were allowed. The study reported an intention to treat (ITT) and modified ITT analysis of 94% and 99% for SVR12. There were no changes in hemoglobin or other adverse events or erythropoietin use in the immediate treatment group compared to placebo. Four percent of patients in the deferred treatment group discontinued treatment due to an adverse event, mainly headache, nausea or fatigue (17). In summary, a regimen of grazoprevir and elbasvir could be an effective regimen to treat HCV genotype 1 infection in patients with severely compromised renal function.

While studies evaluating the safety and efficacy of this regimen in patients with chronic kidney disease have shown success with few adverse events, little is known about the efficacy of this, or any other, therapy in patients on immunosuppression after renal transplantation or whether it is optimal to treat hepatitis c before or after transplantation. Because waiting until after transplant to treat patients for HCV is advantageous by allowing those patients to receive HCV-positive donor organs, most centers are waiting to treat these patients. In order to observe whether there is any difference immunologically or clinically in treating patients before or after renal transplantation, we will compare our transplant cohort to a cohort of historical, non-transplant patients treated for HCV in whom we have stored blood samples from prior IRB-approved studies.

Significance

The prevalence of chronic hepatitis C in patients with CKD is much higher than that observed in the general population (18). This highlights the importance of finding a ribavirin free regimen that is not excreted through the kidneys. However, it is unclear what the timing of HCV therapy should be for these patients.

Additionally, the effect of immunosuppression on the host response to HCV therapy is unknown. On the one hand, these patients could be treated for hepatitis C infection prior to renal transplantation to avoid the impact of immunosuppression as well as the impact of HCV-related liver and kidney disease on allograft function post transplantation. On the other hand, this approach will eliminate access to HCV positive kidneys (making the wait list time longer) and potentially reduce the efficacy of DAA therapy (due to drug-drug interaction between calcineurin inhibitors and HCV drugs). Recent studies have shown that grazoprevir is a weak inhibitor of CYP3A4 and may increase tacrolimus levels (approx. 40% above expected), though change has not been seen in elbasvir or grazoprevir levels (19) (8).

There are real benefits in waiting to treat HCV in patients until after transplantation in that it could decrease the wait time for transplantation by not necessitating a delay in transplant while completing HCV therapy and by permitting the use of HCV-positive kidney donors. Showing the impact that immunosuppression has on the host immune response to HCV during therapy would enable clinicians to decide whether patients should be treated before or after transplant, especially in cases where the wait for a transplant may be quite long.

2.3 Study Design	Experimental design The study will be a pilot, prospective, single-center, open-label, non-randomized, non-controlled clinical trial. 25 HCV genotype 1 infected post-renal transplant patients will be enrolled in the study. Recruitment will be conducted through the renal transplant and nephrology outpatient clinics at the University of Maryland.
-------------------------	--

Study population

The study will involve a single cohort of post-renal transplant patients.

All patients will have HCV genotype 1 chronic infections with active viremia and have no cirrhosis at the time of enrollment. All patients will additionally have stable renal function.

[figure not shown]
The post-transplant patients will include renal transplant recipients of both living donor and deceased donor organs infected with HCV prior to their transplantation with stable GFRs and active HCV viremia. These patients will also be recruited from the University of Maryland's multidisciplinary transplant nephrology clinic.

Inclusion criteria

- At least 18 years of age at the time of screening
- Have stable renal function for one month (30 days) prior to enrollment
- Have Chronic HCV infection prior to transplantation
 - Documented HCV viremia \geq 1,000 IU/ml at screening
 - Either documented HCV Ab positivity or HCV viremia \geq 1,000 IU/ml at least 6 months prior to enrollment
- Documented genotype 1 HCV infection prior to enrollment and after their transplant in the post-transplantation cohort
- HCV disease staging within 12 months prior to enrollment by liver biopsy, transient elastography, or biochemical testing
- Be able to give informed consent and comply with study guidelines
- Women of childbearing age will be required to have a negative pregnancy test at enrollment and use birth control throughout the duration of treatment.
- Patients will have undergone renal transplantation no greater than five years prior to enrollment, and will be followed in our University's nephrology and infectious disease clinic. They will all have stable renal function at the time of enrollment.

Exclusion criteria

- Documented positive HBsAg, and/or HBV DNA prior to enrollment
- Any prior exposure to HCV protease inhibitor therapy
- HIV co-infection if on a protease inhibitor, etravirine or efavirenz based regimen or elvitegravir/cobicistat/emtricitabine/tenofovir disoproxil fumarate
- Increase in creatinine of 15% or greater within one month (30 days) of the screening visit
- Evidence of HCC at the time of enrollment
- Liver disease caused by an etiology other than HCV
- F4 or decompensated cirrhotic patients
- Child Pugh class B or C
- AST or ALT >350 within 6 months prior to enrollment
- Albumin $< 3\text{g/dL}$ at the time of enrollment
- Platelet count $< 75,000$ at the time of enrollment
- History of clinically significant allergy or adverse event with protease inhibitors
- Evidence of the acquisition of HCV at the time of or after transplantation
- Pregnant or breastfeeding women
- Cyclosporine; St. John's Wort; Efavirenz; Phenytoin; Carbamazepine; Bosentan; HIV Protease Inhibitors; modafinil; Ketoconazole; or Rifampin use within 7 days of enrollment
- Coadministration of more than 20 mg atorvastatin; 10 mg rosuvastatin; 20 mg of fluvastatin, lovastatin or simvastatin

	RAV testing (for NS5A positions 28, 30, 31 or 93) will be performed for all patients with HCV genotype 1a infection at the time of enrollment as per clinical recommendations (20).
